6.1.1.3 Adverse Event or Concomitant Medications Dates or Times

For AEs or concomitant medications with missing or partially missing start/stop date/time, the following imputation rules will be applied:

For partial start date/time:

- If the year is unknown, then the date will be assigned the year of the first dose of study treatment. If the entire study is conducted within the same year, then that year will be the imputed year.
- If the month is unknown, then, if the year matches the year of the dose of study drug date, then the month and day of the dose of study drug date will be used to impute the missing month and corresponding day. Otherwise, 'January' will be assigned.
- If the day is unknown, then, if the month and year match the month and year of the dose of study drug date, then the day of the dose of study drug date will be imputed. Otherwise, '01' will be assigned.
- If the time is unknown, then, if the date (day, month, and year) matches the date of the administration of study drug, then the end time of the study drug administration will be imputed. Otherwise, '00:00' will be assigned.

For partial stop date/time:

- If the year is unknown, then the date will be assigned the year that subject discontinued from study, and time will be set to the last time of the day ('23:59').
- If the month is unknown, then month subject discontinued from study will be assigned.
- If the day is unknown, then the last day of the month will be assigned.
- If the time is unknown, then the last time of the day will be assigned ('23:59'), with the exception of end times for epoch in any CDISC dataset, where next day and '00:00' would be assigned.

6.1.1.4 Adverse Event Severity or Relationship to Study Drug

If severity of an AE is not reported, then for tables of AEs by severity, the event will be classified as 'Severe'. If relationship to study drug is not reported for an AE, then for tables of study-drug related treatment emergent AEs, the event will be assigned the relationship 'definite'. If the AE starts before study drug administration, then the relationship 'unrelated' is presumed. Tables presenting related AEs will include all AEs with relationships of 'possible', 'probable' or 'definite' as assessed by the investigator.

If severity or relationship is missing, then a sub-row will be added in the summary tables for imputed vs. severe or imputed vs. related.

6.1.1.5 Time of Events

For calculating the time of an event when only the hour is reported, the minutes will be set to zero.

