Treatment-emergent adverse events (TEAEs) are those with onset on or after the start time of study drug administration, and before or at the end of the study (expected to be Study Day 30 ± 3 days).

Time 0 (zero)

Time 0 is defined as the time of the end of study drug administration, with the exception of AE's and concomitant medications. Time 0 for AE's and concomitant medications are defined as the time of the start of study drug administration.

Time Deviation

For PK sampling time window, *Time Deviation* is the difference (actual – start/end of target window of assessment) between the actual and target window of assessment in the PK sampling. If sampling occurred before the beginning of target window of assessment, time deviation will be calculated by subtracting the actual time from the beginning of the target window of assessment. If the sampling occurred after the end of target window of assessment, time deviation will be calculated by subtracting the actual sampling time from the end of the target window of assessment. Any samples occurring with the target window will have a time deviation of 0.

Baseline

Baseline measurement or assessment is defined as the last available measurement or assessment prior to the start of study drug administration.

Last Follow-up Time

For subjects who withdraw prematurely, the last follow-up time will be defined as the maximum of the last pain or any other study assessment, the last concomitant medication start or end datetime, and the last adverse event start or end datetime.

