6.8.4 Adverse Events

Adverse events will be coded using the Medical Dictionary for Regulatory Activities (MedDRA).

An AE will be considered TEAE if the onset date and time is between the start time of study drug administration and the final Day 30 visit.

If an AE has a partial onset date and time the imputed start and stop dates and times will be used to determine treatment-emergence (e.g., stop date and time is before start time of study drug administration). All AE summaries will present TEAEs only; AEs that are not treatment-emergent will be included in listings but not summarized.

The incidence of subjects reporting TEAEs will be tabulated by the number and percentage of subjects reporting the TEAE. Incidence is defined as a subject reporting at least one TEAE within the summary level. Summary levels are 'at least one TEAE', System Organ Class (SOC) and Preferred Term. Subjects will be counted only once within each reporting level on the table. For example, if a subject reports a TEAE of headache on two separate occasions, the subject will be counted only once in the headache row of the table. Similarly, if a subject reports two separate TEAEs within the same SOC the subject will only be counted once in the summary row for that SOC. A summary of subjects reporting at least one TEAE during the study will also be presented.

The first row on every TEAE table will be the number and percentage of subjects reporting at least one TEAE. Subsequent rows will be presented in descending order of subject counts for the overall within each age group and treatment group, with the most common system organ class first, followed within each SOC by the PT in descending subject count order. For tables presenting the severity or relationship to study treatment of AE, the sort order will be determined by the number and percentage of subjects reporting the PT, thus the sort order of rows will remain the same for the relation or severity tables as the tables by preferred term.

The following summaries will be presented for the AEs reported by the subjects:

An overview of all TEAEs, serious TEAEs and TEAEs of Special Interest will present the number and percentage of subjects in the following categories:

- Any TEAE
 - Maximum severity: Mild
 - o Maximum severity: Moderate
 - Maximum severity: Severe
- At least one related TEAE
- At least one serious TEAE
- At least one TEAE of special interest
- Subjects discontinued due to a TEAE

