6.9.2.1 Time to First Postsurgical Use of Opioid Medication

Time to first postsurgical use of opioid rescue medication will be computed in hours as the date and time of the first opioid rescue medication minus the date and time of the end of surgery. If a subject is not administered an opioid rescue medication, the time to first administration will be censored at 72 hours after surgery or at the time of last follow-up, whichever is earliest. Time to first opioid consumption will be summarized by the quartiles (25th, 50th, and 75th), minimum and maximum estimated using Kaplan-Meier methods within age group and part of the study. The quartile and the 95% confidence limits (CONFTYPE=LOGLOG) for each quartile will be presented.

A Kaplan-Meier plot of the time from end of surgery to first opioid rescue medication use will be presented within age group and part of the study, and a log-rank test p-value of treatment difference shown for group 1.

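### The SAP's hour-only rule can place an adverse event or opioid dose from the clock hour of time zero before time zero, while its rules for wholly missing times keep the same record after it

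*SAP*

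**What the plan says.** **Hour-only times.** SAP 6.1.1.5 consists of one rule: "For calculating the time of an event when only the hour is reported, the minutes will be set to zero". It makes no exception for the clock hour of dosing or of end of surgery.

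**AEs.** SAP Section 4 says: "Treatment-emergent adverse events (TEAEs) are those with onset on or after the start time of study drug administration", up to the end of the study. It also says: "Time 0 for AE's and concomitant medications are defined as the time of the start of study drug administration". Section 6.8.4 adds: "If an AE has a partial onset date and time the imputed start and stop dates and times will be used to determine treatment-emergence". Under the same section, AEs that are not treatment-emergent are listed but not tabulated. Under 6.1.1.4, an AE with no reported relationship is assigned 'definite', but one that starts before study drug is presumed 'unrelated'.

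**Opioids.** SAP 6.9.2 sums doses taken after surgery. Section 6.9.2.1 computes time to first use as the time of the first rescue dose "minus the date and time of the end of surgery". The table shells also set time 0 at the end of surgery.

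**Wholly missing times.** For an AE dated on the day of dosing with unknown time, 6.1.1.3 says "then the end time of the study drug administration will be imputed". For a Day 1 rescue opioid with no time recorded, 6.1.1.1 imputes the end of surgery.

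**The concern.** Setting minutes to zero can only move a record earlier or leave it in place. Within the clock hour that contains time zero, the move can carry a record across the boundary that decides how it is classified. The plan's own direction is the opposite: where the time is wholly missing, it places the record at or after time zero. A record with more information, the hour, is thus treated less conservatively than one with none.

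Safety is the secondary objective. The AEs exposed to the rule begin during infiltration or shortly after it, within the 0 to 2 hour window where Protocol 7.3 puts the first concentration peak in infiltration studies. An AE moved before dosing leaves every summary table, and if its relationship is missing, the default turns from 'definite' to 'unrelated'. For opioids, the result is a negative time to first use, for which the SAP gives no handling rule.

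**Working it through.** The plan states no figure on this point, so there is none to reproduce. The check applies the rules to clock times and then counts how often the boundary is crossed.

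**1. Worked example.** Assumed clock times: study drug starts 10:20 and ends 10:30; surgery ends 11:10.

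| Record | SAP rule | Imputed time | Relative to its time 0 | Result |
|---|---|---|---|---|
| AE at 10:45, recorded as hour 10 | 6.1.1.5 | 10:00 | 10:00 − 10:20 = −20 min | Not treatment-emergent |
| Same AE, no time recorded | 6.1.1.3 | 10:30 | 10:30 − 10:20 = +10 min | Treatment-emergent |
| Opioid at 11:40, recorded as hour 11 | 6.1.1.5 | 11:00 | 11:00 − 11:10 = −10 min (true value +30) | Negative time to first use |
| Same dose, no time recorded | 6.1.1.1 | 11:10 | 0 min | Postsurgical |

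**2. How often the boundary is crossed.** Let time zero fall at minute m of its hour (m = 0 to 59) and the event d minutes later (d = 0 to 59), all combinations equally weighted. The uniform minutes are an assumption.

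- All combinations: 60 × 60 = 3600.
- Event in the same clock hour as time zero: sum of (60 − m) over m = 1830.
- Of these, not moved before time zero: only those with m = 0, which is 60.
- Moved before time zero: 1830 − 60 = 1770, and 1770/1830 = 96.7%.
- As a share of all hour-only events in the first 60 minutes: 1770/3600 = 49%.

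These are shares of hour-only records, not of all records.

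**3. Effect of a floor.** Replace the imputed time by the later of hh:00 and time zero when the two share a clock hour. Then 0 of the 1830 cases fall before time zero.

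**4. Price of the floor.** On the same grid, the minutes of that clock hour lying before time zero number sum of m = 1770, against 1830 at or after it. If events were spread evenly over the hour, 1770/3600 = 49% of hour-only events in it would truly precede time zero, and the floor would count them as on or after it.

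**5. Weight of one subject.** 1/15 = 6.7 percentage points in one arm of one part; 1/30 = 3.3 points with Parts 1 and 2 combined.

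**The case against.** **The trigger may be rare.** Protocol 14.1.2 collects date and time of AE onset, and 13.5 collects date, time and amount of each opioid. The listing shells print hours and minutes. Nothing shows that an hour-only record exists. This stands and limits the size of the point. The sponsor nevertheless wrote a rule for such records, and the rule should work.

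**6.1.1.3 may already govern.** It is introduced as covering partially missing times as well as missing ones. However, its time rule applies when the time is unknown, and 6.1.1.5 is the specific rule when the hour is known. No order of precedence is given. A reader might call this a direct contradiction; it is better described as an unclear boundary between two rules that lean in opposite directions.

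**A reader might infer that affected AEs vanish from the report.** They do not. Section 6.8.4 keeps them in listings, and the SAP plans listings of all AEs, all serious AEs, and AEs of special interest as the protocol defines them. The loss is from the tables.

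**A reader might infer that an hour-only stop time also removes an AE**, because 6.8.4 gives as its example "stop date and time is before start time of study drug administration". It does not: that section uses imputed times only where the onset is partial. An AE with a complete onset after dosing stays treatment-emergent.

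**A reader might infer that early opioid doses are discarded, or that median times shift materially.** Section 6.1.1.1 expects complete rescue times, provides for queries, and then allows conservative case-by-case imputation. Section 6.9.2 draws on a postsurgical pain medication page, so a dose can be known to be postsurgical whatever its imputed minute. What remains is the literal negative time. A shifted median would require assuming what share of records is hour-only and that staff truncate rather than round; the documents give neither.

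**Conclusion.** Wrong as written, and minor. Read literally, 6.1.1.5 together with Section 4 and 6.8.4 classifies a post-dose AE as pre-dose when it is recorded only by the clock hour of dosing, unless dosing began exactly on the hour. The same AE with no time would be tabulated. The opioid case is parallel but softer, because 6.1.1.1 and the postsurgical medication page offer a way round it.

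The total effect scales with the unknown number of hour-only records and may be nil. Where such a record occurs in the first hour after time zero, the chance that it crosses the boundary is about one half under uniform minutes. In arms this small, a single subject is visible in an incidence table. All summaries of these data are descriptive apart from one log-rank p-value on time to first opioid in Group 1, the opioid endpoints are exploratory, and no primary conclusion depends on the rule.

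The argument is not that the present rule misclassifies more often than a floor would: the grid counts are similar in both directions. It is that the error should fall on the conservative side, which the SAP has already chosen for wholly missing times.

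**What to change.** Add to SAP 6.1.1.5:

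> If the reported hour and date are those of the start of study drug administration (AEs, concomitant medications) or of the end of surgery (opioids recorded as postsurgical), an hour-only start time is set to the later of hh:00 and that reference time, unless other recorded data show that the event came first. This rule takes precedence over 6.1.1.3 for hour-only times.

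The cost is one added provision and a small programming change. The downside is that some hour-only events from just before dosing in that clock hour, including intraoperative ones, will be counted as treatment-emergent. That is the direction 6.1.1.3 already takes, and the exception for other recorded data limits it where the order of events is known.

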6.2 Subject Disposition

Subject disposition summaries will include the number of subjects that were:

- Screened
- Randomized
 - o Randomized, not treated
 - o Randomized and treated
- In the safety population

- In the PK population
- Completed the study as planned
- Discontinued from the study, and
 - Reasons for discontinuation from the study

Percentages will be based on the number of subjects randomized.

6.3 Description of Demographics and Baseline Characteristics

6.3.1 Demographics

The summary of demographic data will present:

- Age (years) descriptive statistics
- Sex -n (%)
- Ethnicity n (%)
- Race n (%)

Demographics in the PK Population and the Safety Population will be summarized by treatment group (EXPAREL or Bupivacaine HCl) for Group 1 and by surgery type (cardiac or spine) for Group 2.

6.3.2 Baseline Characteristics

The summary of baseline characteristic data will present:

- American Society of Anesthesiologists (ASA) Classification
- Baseline pain intensity scores
- Height (cm)
- Weight (kg)
- Body Mass Index (BMI) (kg/m²)

The formula for BMI is $w/(h^2)$, where w is weight in kilograms and h is height in meters. Weight in pounds will be converted to kilograms using the conversion factor of 2.2046 pounds to 1 kilogram. Height in inches will be converted to centimeters using the conversion factor of 2.54 centimeters to 1 inch. Height in centimeters will be converted to meters using the conversion factor of 100 centimeters to 1 meter.

Baseline characteristics summarizes will be summarized by treatment group for Group 1 and by surgery type for Group 2.

Descriptive statistics (n, mean, SD, median, minimum and maximum) will be provided for pain scores, height, weight, and BMI at baseline. The number and percent of subjects will be tabulated for the various categories of ASA classification.

6.4 Surgery Characteristics

Surgery characteristics include duration of surgery and total incision length. Duration of surgery is calculated as the difference between the end of surgery and start of surgery times and reported in hours. Descriptive statistics will be provided for the duration of surgery and total incision length using the safety population, by treatment group for Group 1, and by surgery type for Group 2. Surgical characteristics will be included in data listings.

6.5 Intraoperative, Prior, and Concomitant Medications

Intraoperative, Prior, and concomitant medications will be coded using the World Health Organization Drug Dictionary (WHO-DD) and will be classified according to the default anatomical therapeutic chemical (ATC 4) classification term and preferred term (PT).

Intraoperative medications are medications collected on Intraoperative Medication eCRF page. Intraoperative medications are defined as medications given as part of the surgical procedure. These may include anesthesia, opioids or other medications with start and stop dates on the day of surgery and start times overlapping within the surgery start and stop times.

Prior medications are defined as medications with a stop date and time prior to the start of surgery. Prior medications are recorded on the prior/concomitant medication eCRF page.

Concomitant medications are defined as medications taken after the start of study drug administration (i.e., started prior to the start of study drug administration and continued after or started after the start of study drug administration) and recorded on the prior/concomitant or post surgical pain medication CRF page.

Intraoperative, prior and concomitant medications will be summarized separately using the number and percentage of subjects within each age group and treatment group of the study by ATC class and PT for the safety population. Subjects may have more than one medication per ATC category and PT. At each level of subject summarization, a subject will be counted once if one or more medications are reported by the subject at that level.

A data listing will be created for all medications, with a flag variable identifying intraoperative, prior, and concomitant medications.

A listing mapping the ATC class and PT to verbatim term will be presented.

6.6 Measurements of Treatment Compliance

Study treatment is administered by a party other than the subject, therefore compliance is assured.

6.7 Pharmacokinetic Analysis

6.7.1 Sample Collections for Pharmacokinetic Analysis

A sparse PK sampling scheme is used to limit the number of blood draws from individual subjects. On Day 1, eligible subjects will be assigned to one of two PK sampling groups shown in Table 2 based on surgery type. A total of 8 blood samples will be collected from each subject at the specific time windows shown for the determination of bupivacaine plasma concentrations.

Surgery	y PK Sample Timing (Based on the End of Study Drug Administration)							
Туре	Sample 1	Sample 2	Sample 3	Sample 4	Sample 5	Sample 6	Sample 7	Sample 8
Spine	15±5 min	30±5 min	45±5 min	1-1.25 h	2-3 h	10-18 h	24-36 h	42-60 h
Cardiac	15±5 min	30±5 min	45±5 min	1-1.25 h	15-25 h	30-40 h	45-55 h	64-72 h

Table 2PK Sampling Times

Abbreviations: h = hour; min = minutes; PK = pharmacokinetic

These sampling time points will not only characterize overall PK of bupivacaine from EXPAREL, but will also characterize the PK of immediate release bupivacaine and thoroughly characterize the early peak for both surgery types.

6.7.2 Pharmacokinetic Parameters Calculation Methods

Nonsterospecific assay is used for the measurement of bupivacaine concentration. Pharmacokinetic parameters will be calculated by noncompartmental analysis (NCA) method from concentration-time data following these guidelines:

- Actual sampling times relative to study drug administration will be used for all calculations of the PK parameters. If there is any doubt as to the actual time a sample was taken, then the scheduled time will be used.
- Concentrations from unscheduled PK blood samples will be used in the analysis of the parameters.
- There will be no imputation of missing concentration data.
- For the summaries of concentrations and for calculation of area under the curve (AUC) from bupivacaine plasma concentrations, concentrations below the limit of quantification (BLOQ) will be handled as follows:
 - Pre-dose values will be set to zero.
 - BLOQ values between the dosing time and the first time point above lower limit of quantification (LLOQ) will be set to 0.
 - BLOQ values at time points between two measurable concentration values will be set to ½ of LLOQ (lower limit of quantification).
 - All remaining BLOQ values will be set to missing.

The following PK endpoints will be determined using non-compartmental methods:

- Area under the plasma concentration-versus-time curve (AUC0-∞ and AUC0-last). The AUC0-last from the time of dosing to the time of the last quantifiable concentration will be calculated using the linear trapezoidal method. The AUC0-∞ from the time of dosing (zero) to infinity will be calculated as sum of AUC0-last and residual area Ct/λz.
- Maximum plasma concentration (Cmax) and time of Cmax (Tmax).
- The apparent terminal elimination half-life (t1/2el). t1/2el will be calculated as $\log_e(2)/\lambda_z$. The apparent terminal elimination rate constant (λ_z) will be estimated at terminal phase by linear regression after log-transformation of the concentrations:
 - Only those data points that are judged to describe the terminal log-linear decline will be used in the regression.
 - A minimum number of three data points in the terminal phase will be used in calculating λ_z with the line of regression starting post the Cmax data point (Cmax will not be part of the regression slope) and including the last point above LLOQ value (Ct).
 - An appropriate number of decimal places will be used for λ_z to enable the reported value of terminal half-life (t1/2el) to be calculated.
- Apparent clearance (CL/F) will be estimated as Dose/AUC0-∞.
- Apparent volume of distribution (Vd/F) will be estimated based on the teriminal phase as Dose/($\lambda_z \cdot AUC0-\infty$).

In addition, a population PK modeling will be performed using all PK data collected during the study. The population PK analysis plan will be developed separately.

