6.7.3 Pharmacokinetic Concentrations and Variables

A complete data listing will be provided for all PK bupivacaine concentration data. Concentrations that are BLOQ will be indicated in the listing.

A plot of bupivacaine concentration-time data, with original scale and semi-log scale overlain on the same page will be created for each individual subject.

If different than the preceding plot, a plot of dose-normalized concentration-time data, with the original scale and semi-log scale overlaid on same page, will also be created for each individual subject.

Plasma bupivacaine concentrations for each formulation will be summarized at each nominal time window (any out-of-window results would be shown only in a listing). The following descriptive statistics

will be presented: n, geometric mean, arithmetic mean, SD, %CV, median, minimum and maximum. Results will be summarized by treatment group (EXPAREL or bupivacaine HCl) for Group 1 and by surgery type (cardiac or spine) for Group 2. Plots of mean bupivacaine concentration over time will be created with the original scale and semi-log scale overlain on the same page. If the number of subjects in a group is less or equal to 3, then individual concentration over time curves will be plotted instead of the mean concentration. For group 1, there will be two plots overlain for the two treatments. For group 2, there will be two separate plots for the two types of surgery.

Pharmacokinetics parameters will be presented in the data listings and descriptive summary statistics, including the arithmetic mean, median, minimum, maximum, standard deviation, %CV of mean, geometric mean, %CV of geometric mean. Differences will be compared between the two formulations using single factor ANOVA.

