	Mean (%CV)	xx.x (xx.x)	xx.x (xx.x)
	SD	x.xx	X.XX
	Median	XX.X	XX.X
	Geometric Mean (%CV)	XX.X	XX.X
	Minimum, Maximum	XX, XX	XX, XX
	p-value *	0.xxx	
AUC(0-last) (hr*ng/mL)	n	XX	XX
	Mean (%CV)	xx.x (xx.x)	XX.X (XX.X)
	SD	x.xx	X.XX
	Median	XX.X	XX.X
	Geometric Mean (%CV)	XX.X	XX.X
	Minimum, Maximum	XX, XX	XX, XX
	p-value *	0.xxx	

* 2-sided t-test

Source: list SAS datasets used to create table SAS X.Y

ddmmmyyyyThh:mm program name

Note to programmer: Other Pharmacokinetic parameters to appear on this table are, in order of

appearance: Cmax (ng/mL), Tmax, t1/2el (hr), CL/F (L/hr), and Vd (L). Use this template also for tables:

Table 14.4-1.2: Summary of EXPAREL Pharmacokinetic Parameters (Group 2: 6 to < 12 years) - Spine Surgery - PK Population

Table 14.4-1.3: Summary of EXPAREL Pharmacokinetic Parameters (Group 2: 6 to < 12 years) - Cardiac Surgery - PK Population

Table 14.4-1.4: Summary of EXPAREL Pharmacokinetic Parameters (Both Groups: 6 to < 17 years) - Spine Surgery - PK Population

(Page X of Y)

Protocol: 402-C-319

Table 14.4-3.1: Summary of EXPAREL Pharmacokinetic Plasma Concentrations (ng/mL) (Group 1: 12 to <17 years) - PK Population

		EXPAREL	Bupivacaine HCl
	Statistic	[N=XX]	[N=xx]
15 Minutes	n	XX	XX
	Mean (%CV)	xx.x (xx.x)	xx.x (xx.x)
	SD	X.XX	X.XX
	Median	XX.X	XX.X
	Geometric Mean (%CV)	xx.x (xx.x)	xx.x (xx.x)
	Minimum, Maximum	XX, XX	XX, XX
30 Minutes	n	XX	xx
	Mean (%CV)	xx.x (xx.x)	xx.x (xx.x)
	SD	X.XX	X.XX
	Median	XX.X	XX.X
	Geometric Mean (%CV)	xx.x (xx.x)	xx.x (xx.x)
	Minimum, Maximum	XX, XX	XX, XX

Source: list SAS datasets used to create table

ddmmmyyyyThh:mm

SAS X.Y

program name

Note to programmer: Other Pharmacokinetic Plasma Concentration timepoints to appear on this table are, in order of appearance: 45 Minutes, 1 - 1.25 Hours, 2 - 3 Hours, 10 - 18 Hours, 24 - 36 Hours, and 42 - 60 Hours. Use this template also for tables:

Table 14.4-3.2: Summary of EXPAREL Pharmacokinetic Plasma Concentrations (ng/mL) (Group 2: 6 to < 12 years) - Spine Surgery - PK Population

Table 14.4-3.3: Summary of EXPAREL Pharmacokinetic Plasma Concentrations (ng/mL) (Group 2: 6 to < 12 years) - Cardiac Surgery - PK Population

Note to programmer: Change timepoints to: 15 Minutes, 30 Minutes, 45 Minutes, 1 - 1.25 Hours, 15 - 25 Hours, 30 - 40 Hours, 45 - 55 Hours, and 64 - 72 Hours.

Table 14.4-3.4: Summary of EXPAREL Pharmacokinetic Plasma Concentrations (ng/mL) (Both Groups: 6 to < 17 years) - Spine Surgery - PK Population

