Figure 1.1.1 Plot of Time to First Rescue Medication Use (Group 1: 12 to <17 years) - Safety Population

[figure not shown]
Note to programmer: Time to first rescue on x-axis 0-72 Hours by 12. Overlay both treatments for Group 1. For table underneath plot, provide for each treatment in Group 1 with a header for treatment. Add footnote: "Subjects who are not administered an opioid rescue medication by 72 hours are censored at 72 hours after surgery or at the time of last follow-up, whichever is earliest."

Use this template for the following figure:

Figure 1.1.2 Plot of Time to First Rescue Medication Use (Group 2: 6 to < 12 years) - Safety Population

Note to programmer: Time to first rescue on x-axis 0-72 Hours by 12. Overlay both surgery types for Group 2. For table underneath plot, provide for each surgery type in Group 2 with a header for surgery type. Add footnote: "Subjects who are not administered an opioid rescue medication by 72 hours are censored at 72 hours after surgery or at the time of last follow-up, whichever is earliest."

Figure 2.1.1 Plot of Mean (± SD) Bupivacaine Concentrations (ng/mL) over Time (Group 1: 12 to <17 years) - PK Population - Linear Scale

Note to programmer: Overlay both treatments for Group 1. For Samples 4-8, use the midpoint of the collection window for the tick mark (i.e. 1.125 for 1-1.25 window). Label the tick mark with the time window (i.e. "1-1.25 hr"). Change the y-axis label to "Bupivacaine Concentration (mg/mL)".

Add footnotes: "For concentrations below the limit of quantification (BLOQ), pre-dose values are set to zero, BLOQ values between the dosing time and the first time point above lower limit of quantification (LLOQ) are set to 0, BLOQ values at time points between two measurable concentration values are set to ½ of LLOQ (lower limit of quantification), and all remaining BLOQ values are set to missing. For Samples 4-8, the midpoint of the collection window is used for the tick mark. "

Use this template for the following figures:

Figure 2.1.2 Plot of Mean (± SD) Bupivacaine Concentrations (ng/mL) over Time (Group 2: 6 to < 12 years) - Spine Surgery - PK Population - Linear Scale

Figure 2.1.3 Plot of Mean (\pm SD) Bupivacaine Concentrations (ng/mL) over Time (Group 2: 6 to < 12 years) - Cardiac Surgery - PK Population - Linear Scale

Figure 2.1.4 Plot of Mean (± SD) Bupivacaine Concentrations (ng/mL) over Time (Both Groups: 6 to < 17 years) - Spine Surgery - PK Population - Linear Scale

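### Setting trailing BLOQ concentrations to missing biases the late-window concentration summaries and mean plots upward; the NCA parameters are not affected

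*SAP*

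**What the plan says.** SAP 6.7.2 states the scope of its BLOQ rules in these words: "For the summaries of concentrations and for calculation of area under the curve (AUC) from bupivacaine plasma concentrations". Pre-dose and leading BLOQ values become 0. For embedded ones, "BLOQ values at time points between two measurable concentration values will be set to ½ of LLOQ". Then: "All remaining BLOQ values will be set to missing". Since the other cases have their own rules, what remains is the trailing values. The same section adds "There will be no imputation of missing concentration data", so these values drop out of n and of every statistic.

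SAP 6.7.3 applies this to the tables: "Plasma bupivacaine concentrations for each formulation will be summarized at each nominal time window", and the statistics that "will be presented: n, geometric mean, arithmetic mean, SD, %CV, median, minimum and maximum". Neither that list nor the Table 14.4-3.1 mock-up has a count of BLOQ values; BLOQ is marked only in the listing. The late windows for spine surgery, shared by both Group 1 arms, are "10 - 18 Hours, 24 - 36 Hours, and 42 - 60 Hours". The Figure 2.1.1 footnote, for the overlaid Group 1 mean curves, says that "all remaining BLOQ values are set to missing".

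**The concern.** The rule suits AUC0-last, which stops at the last quantifiable value, and lambda-z, whose regression ends there. A by-window summary is different. A trailing BLOQ result is an observation known to lie below the LLOQ. Dropping it leaves the higher values to represent the whole arm.

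The rule also treats identical results differently within one table cell. At 24-36 h, a BLOQ result counts as LLOQ/2 if the subject has a later quantifiable sample, and disappears if not.

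At stake is the description of late exposure. SAP 6.7.1 says the sampling is also meant to characterise immediate-release bupivacaine, so the comparator's late windows are an intended output. A reader who sees a smaller n cannot tell from the table whether samples were BLOQ, not drawn, or out of window (out-of-window results are shown only in the listing).

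**Working it through.** The plan gives no LLOQ, BLOQ share or concentration variance, so there is no figure to reproduce. The direction follows from the text; the size needs assumptions.

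**1. Direction.** In the last window (42-60 h spine, 64-72 h cardiac) a BLOQ value can be embedded only if a later unscheduled sample is quantifiable. Otherwise every BLOQ there is dropped, and the reported mean, median and minimum cannot fall below the LLOQ. In earlier late windows the bias is partial, because embedded values stay in as LLOQ/2.

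**2. Size in one window.** Assume lognormal concentrations, a share q below the LLOQ, all of it trailing. Let s = √ln(1+CV²) and z = Φ⁻¹(q), and express concentrations in LLOQ units.

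- Reported/true arithmetic mean: R = [1 − Φ(z − s)]/(1 − q)
- Reported/true geometric mean: exp[s·φ(z)/(1 − q)]
- True mean: M = exp(−s·z + s²/2); absolute inflation: (R − 1)·M
- Reported/true mean with LLOQ/2 substituted: [1 − Φ(z − s)] + 0.5·q/M
- Reported/true mean with 0 substituted: 1 − Φ(z − s)

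CV 60% gives s = 0.5545 and CV 100% gives s = 0.8326; z = −0.2533 at q = 40% and +0.2533 at 60%.

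| CV | q | R | GM ratio | Inflation (LLOQ units) | With LLOQ/2 | With 0 |
|---|---|---|---|---|---|---|
| 60% | 40% | 0.7904/0.6 = 1.32 | 1.43 | 0.317 × 1.342 = 0.43 | 0.94 | 0.79 |
| 100% | 40% | 0.8612/0.6 = 1.44 | 1.71 | 0.435 × 1.746 = 0.76 | 0.98 | 0.86 |
| 60% | 60% | 0.6184/0.4 = 1.55 | 1.71 | 0.546 × 1.013 = 0.55 | 0.91 | 0.62 |
| 100% | 60% | 0.7188/0.4 = 1.80 | 2.23 | 0.797 × 1.145 = 0.91 | 0.98 | 0.72 |

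At 10% BLOQ, R is only 1.07-1.09. At 60% BLOQ the true median, exp(−s·z), is 0.87 (CV 60%) or 0.81 (CV 100%) of the LLOQ. The table would print exp[−s·z + s·Φ⁻¹(0.8)], which is 1.39 or 1.63 times the LLOQ.

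**3. By arm.** Both Group 1 arms share the spine windows. Bupivacaine HCl is given at 2 mg/kg and EXPAREL at 4 mg/kg. Protocol 7.3 says plain bupivacaine usually acts for under 8 h and puts a second EXPAREL peak at roughly 24-48 h. That suggests more BLOQ in the comparator.

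As illustration, the SAP rules were simulated with inputs that are not in the documents: an immediate-release level of about 500 ng/mL early with mono-exponential decline, an EXPAREL depot peak of about 250 ng/mL at 30 h, between-subject CV 50%, and LLOQ 1, 5 or 10 ng/mL. For bupivacaine HCl at 42-60 h:

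| Assumed half-life | BLOQ | Reported/true mean |
|---|---|---|
| 12 h | 1-21% | 1.01-1.23 |
| 8 h | 15-64% | 1.17-2.28 |
| 5 h | 65-96% | 2.6-9.5 |

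At a 3 h half-life, 98-100% is BLOQ and fewer than one of 15 subjects is expected to remain. EXPAREL had 0% BLOQ and a ratio of 1.00 in every scenario.

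**4. Absolute size in the simulation.** The spread within a window is wider here than in step 2, so the inflation can exceed one LLOQ. With half-life 5 h and LLOQ 10 at 24-36 h (57% BLOQ), it is 30.74 − 15.37 = 15.4 ng/mL, or 1.5 LLOQ. Against an EXPAREL mean of 284.35, the difference between arms goes from 268.98 to 253.61, a loss of 5.7%.

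**The case against.** By-window means are descriptive. Protocol 12.2 lists model-predicted AUC, Cmax, half-life, CL/F and Vd/F as the PK endpoints, and SAP 6.7.2 leaves population PK to its own plan. AUC0-last, Cmax and lambda-z do not change under this rule. The primary objective concerns EXPAREL, while the bias probably falls mostly on one 15-subject comparator arm. Planned n, the marked listing, individual plots and the figure footnote let a careful reader trace the loss. All of this stands and limits the importance, but the table itself still misstates the late level. The fallback to individual curves depends on three or fewer subjects in a group, not on how many quantifiable values a window holds.

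On size, the ratios apply to a mean near the LLOQ. On a linear overlay the change may hardly show; it matters mainly on the semi-log plot. This also stands.

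A reader might infer more than the documents support:

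- *That the comparator is shown to be hit hardest.* The documents do not say so. The under-8-h figure is duration of effect, not plasma half-life, so the ordering is only a plausible inference.
- *That the plot would show a flat or rising comparator tail.* This is not shown. In the simulated scenarios the reported mean falls too slowly (30.74 to 19.10 ng/mL between the last two windows, against a true 15.37 to 2.00, in the example above), but it still falls in each one.
- *That all late means rest on quantifiable samples alone.* That is strictly so only in the last window.

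**Conclusion.** The point holds as a fault in descriptive reporting. The direction is certain once any trailing BLOQ value is dropped and needs no assay assumption. The size is unknown. At 40-60% BLOQ, with lognormal data and CV 60-100%, the arithmetic mean is 1.3-1.8 times too high and the geometric mean 1.4-2.2 times. In that model the excess is less than one LLOQ; with a wider spread it can be more. With a sensitive assay and slow decline it is negligible (ratio 1.01). The larger effect in the bupivacaine HCl arm is probable, not established. The rule gives no reason to doubt AUC0-last, Cmax or lambda-z. It is worth correcting because the tables and overlays describe PK, the primary objective, and the change is small.

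**What to change.** Split the rule in SAP 6.7.2 and carry it through to the shells:

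- Keep trailing BLOQ as missing for the NCA only.
- In the concentration summaries and mean plots, set post-dose trailing BLOQ to LLOQ/2, matching the embedded-value rule. Do not substitute 0: it gives only 0.62-0.72 of the true mean at 60% BLOQ, against 0.91-0.98 with LLOQ/2.
- Add a number (%) BLOQ row per window and arm to Tables 14.4-3.1 to 14.4-3.4. Samples not drawn stay missing.
- Where more than half the values in a window are BLOQ, suppress the arithmetic and geometric means and report the median as <LLOQ.
- Amend the Figure 2.1.1 footnote, which is the template for Figures 2.1.2 to 2.1.4, and apply the same rule to the semi-log mean plots.

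The cost is a short SAP edit, one table row and one footnote, with no new data. The downside is that LLOQ/2 is itself an approximation and fails when nearly everything is BLOQ: in the simulation with half-life 3 h and LLOQ 1 at 42-60 h, it gave 0.55 against a true 0.12 ng/mL. The suppression rule is there for that case. The BLOQ count is worth adding whatever the LLOQ turns out to be.
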